Official Study Title: Use of liposomal bupivacaine for postoperative pain management after arthroscopic rotator cuff repair

ClinicalTrials.GOV ID Number: NCT03149887

Protocol Date: 2/13/2019

Scientific Background:

Arthroscopic rotator cuff repair is among the most painful of orthopedic surgeries. Hundreds of thousands of these procedures are carried out in the U.S. each year. Many involve the use of a brachial plexus nerve block, which serves to control pain for 12 to 14 hours. However, when the block wears off, many patients are left with severe pain. This severe pain is must then be managed at home with oral opioids, which have numerous undesirable side effects, and may lead to chronic opioid dependence. Thus, any therapy which might reduce the pain burden on these patients and therefore reduce opioid use and side effects, would be advantageous.

Recently, a long-acting form of bupivacaine, prepared in liposomes, has been approved for use by injection in the surgical field, though not for peripheral nerve blockade. The drug has been used to improve postoperative pain after total knee arthroplasty and total hip arthroplasty when injected in the peri-articular tissues by the orthopedist, as well as in other surgeries, both orthopedic and non-orthopedic. Liposomal bupivacaine is FDA approved for administration into the surgical site to produce postsurgical analgesia and mitigate pain, but it hasn't been yet used for rotator cuff surgery.

Study Objectives:

The purpose of this research study is to determine if liposomal bupivacaine, injected into the surgical field during rotator cuff repair surgery provides superior analgesia post operatively (after the standard nerve block resolves) compared with standard therapy.

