The primary outcome measure is pain score at 24 hours, which will be obtained by phone follow up. Secondary outcomes include maximal pain score on postoperative day 1, 2 and 3, total oral opioid morphine equivalent after 3 days, and occurrence of typical opioid side effects (nausea, vomiting, and/or drowsiness). In addition to follow up phone call on POD 1, patients will keep a pain diary, documenting pain scores and opioid use for the first 72 hours, which will be collected by the surgeon in his office at the first postoperative visit. Any adverse occurrences related to nerve blockade or prolonged bupivacaine effect will also be recorded. In addition, the development of chronic pain at the surgical site will be assessed and compared between the two groups, with appropriate referral to the chronic pain service for any patient who experiences this outcome.

Study Design and Methods:

This randomized, double blind, placebo-controlled study was approved by the University of Pittsburgh Institutional Review Board (PRO17020089), and registered with ClinicalTrials.gov (NCT03149887).

Patients will provide written consent for participation on the day of surgery. A computer-generated randomization number will be assigned by the Investigational Drug pharmacy at our institution, and patients will be accordingly designated to receive either liposomal bupivacaine or normal saline injection. The pharmacy will then prepare the study drug (either liposomal bupivacaine or saline), packaged in a fashion that cannot be recognized by the investigators, and then sent to the operating room for injection by the surgeon.

The patients and the research team will be blinded to which group the patients are in. It is not possible to prepare an effective placebo solution for the liposomal bupivacaine, so the surgeon will remain un-blinded. Other members of the research team will determine the primary and secondary outcomes, and the

surgeon will not take part in the data collection for primary or secondary analyses. By the time of the first surgical follow up examination, the outcomes will have been determined and recorded by investigators.

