All patients will undergo standard interscalene nerve blocks with plain bupivacaine 0.5% or ropivacaine 0.5%, with volumes varying between 15 and 20 ml based upon visual analysis of injectate spread by the anesthesiology team. Once an effective nerve block is demonstrated (inability to raise the arm, biceps weakness, loss of sensation over the C4 and C5 dermatome regions), patients are to be taken to the operating room. Anesthesia for the procedure will consist of the interscalene nerve block, along with infusion of propofol for sedation, accompanied by small doses of ketamine (20 to 40 mg), and dexmedetomidine (12-20 mcg).

Per our institutional review board, it is essential that the joint capsule be closed before injection of liposomal bupivacaine, since liposomal bupivacaine is not approved for intra-articular use. If the capsule cannot be closed for surgical reasons at the end of the procedure, an enrolled patient will be removed from the study at that point, and will not receive the injection of the study drug. The rotator cuff repairs are to be performed in the beach chair position by a single surgeon with either three or four routine portals, including anterior, posterior, and one or two lateral portals. The total dose of liposomal bupivacaine will be 266 mg, diluted with an additional 40 ml of saline to a total of 60 ml. In control patients, 60 ml of normal saline are to be injected in like fashion. In each group, the sixty milliliters of solution was divided into two thirty milliliter syringes. After completion of the arthroscopic rotator cuff repair, which includes a subacromial decompression, an eighteen gauge spinal needle will be placed under direct vision into the subacromial space and secured with tape. The arthroscopic instrumentation will be removed and each of the three or four portals then infiltrated at the superficial skin and the deep tissue, including the deltoid muscle surrounding the portal tract, with equally divided amounts from one of the thirty milliliter syringes using a one and one-half inch twenty-two gauge needle. The portals will then be closed with absorbable suture and the remaining thirty milliliters of solution in the second syringe injected into the subacromial space via the previously placed eighteen gauge spinal needle. Finally, the needle is to be removed, and the dressings as well as a sling are applied.

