At the conclusion of surgery, patients will be taken to PACU, where they report their NRS pain score, and intravenous dilaudid will be provided for analgesia for scores greater than 3/10. Patients are to be called the day after surgery (approximately 24 hrs after leaving the hospital), and asked about their pain experience. Specifically, for the primary outcome, they will be asked to relate NRS pain score, at the time that the interscalene block had, in their perception, completely resolved (restoration of hand sensation, movement at elbow, and onset of pain at the shoulder). For the secondary analyses of pain and opioid use, patients will record their NRS scores in a 72 hour postoperative diary, for pain at rest and (for patients instructed to do so) when participating in range-of-motion exercises ("pendulum swings"). In addition, the participants are to record oral opioid doses, use of other analgesics (such as acetaminophen), and any side effects that they encounter. Patients also will rate their satisfaction regarding pain management at the end of the 72 hour period. The pain diary will then be brought to the one-week follow up appointment, collected by the research team, and the data transcribed. Finally, the surgeon will note any patient who develops chronic pain requiring referral to a pain management specialist.

Eligibility Criteria:

Those eligible for inclusion are adults ages 18-65, in American Society of Anesthesiologist physical status class 1 through 3, who are undergoing arthroscopic rotator cuff repair, either primary or revision. Exclusion criteria include pre-existing nerve damage, pre-existing chronic pain in the shoulder joint, opioid use for greater than 30 days preoperatively, coagulopathy, renal or liver disease, pregnancy, allergy

to local anesthetics, patient refusal, infection at the site of injection, age over 65 years, or incompetent rotator cuff/joint capsule.

Statistical Considerations:

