Sample size is calculated based on the a priori assumption that liposomal bupivacaine would result in a reduction of pain scores at the time of block resolution by two or more units in the NRS rating (0 to 10 scale). The minimum clinically important difference for acute pain, acute postoperative pain, and shoulder-related pain range between 1 and 2 (out of 10), We chose a change in the score of 2 units to represent a clinically important improvement in pain control. To detect a decrement of 2 units or more with a two-tailed significance level of 0.05 and a power of 0.8, a sample size of 50 is required, 25 in each group.

The analysis of data will be carried out using SAS software, Version 9.4, of the SAS System for Windows (Copyright 2016 SAS Institute Inc., Cary, NC, USA). Continuous measures, such as pain scores, oral morphine equivalents, and some demographic information, are presented as mean \pm standard deviation, and compared using t-tests. Frequency distributions of categorical variables, such as opioid related side effects, and other demographic information, are compared using the Fisher's exact test. Opioid use will be converted to oral morphine equivalents. A two-tailed p value of <0.05 is considered to reflect statistical significance, while a difference in the primary outcome of 2 or more on the NRS scale is our threshold for clinically meaningful change

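### The primary outcome is given two incompatible time points, and block resolution is described partly by the shoulder pain that the drug is meant to reduce

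*Combined protocol and SAP*

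**What the plan says.** Three sections of the combined protocol and SAP bear on the primary outcome.

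- **Study Objectives:** "The primary outcome measure is pain score at 24 hours, which will be obtained by phone follow up".
- **Study Design and Methods:** patients are phoned the day after surgery, "approximately 24 hrs after leaving the hospital". For the primary outcome they give the NRS score "at the time that the interscalene block had, in their perception, completely resolved". A parenthesis then describes that moment: "restoration of hand sensation, movement at elbow, and onset of pain at the shoulder".
- **Statistical Considerations:** the sample size rests on a "reduction of pain scores at the time of block resolution by two or more units in the NRS rating (0 to 10 scale"), with 25 patients per group, two-sided 0.05 and power 0.8. Pain scores are compared by t-test.

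Two other statements matter. Scientific Background says of the nerve block "which serves to control pain for 12 to 14 hours". Study Design and Methods lists the signs of an effective block before surgery: "inability to raise the arm, biceps weakness, loss of sensation over the C4 and C5 dermatome regions". No section says how to score a patient who has no shoulder pain when the block has gone, and there is no missing-data rule.

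**The concern.** There are two linked problems.

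**Which score is primary.** Pain at 24 hours and pain at block resolution are different measurements, usually many hours apart. The significance test and the 2-unit threshold for a meaningful change attach to the primary outcome, and the plan leaves open which of the two that is. The sample-size assumption was made for only one of them.

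**When the score is taken.** The drug is intended to reduce shoulder pain after the block wears off. If shoulder pain must begin before the block counts as resolved, treatment can delay or prevent the scoring moment. A patient with sensation and movement restored and no pain, which is the best result the drug could give, would then have no primary score or a later one. Whether that happens depends on how the caller reads the parenthesis. The diary scores for the first 72 hours are not tied to pain onset, so the secondary pain data are unaffected.

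**Working it through.** **1. Distance between the two time points.** Inputs: block duration 12 to 14 hours (Scientific Background); call about 24 hours after leaving the hospital (Study Design and Methods). The gap between block resolution and the call is at least 24 − 14 = 10 hours to 24 − 12 = 12 hours, plus the time from placing the block to leaving the hospital. The two definitions therefore do not normally coincide.

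**2. The plan's own figure.** No SD is stated, so 25 per group cannot be reproduced from the documents. It can only be solved backwards.

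- Normal approximation: SD = 2 × √(25/2) / (1.960 + 0.842) = 7.07 / 2.80 = 2.52.
- Two-sample t-test (noncentral t, 48 df): standardised difference 0.809, so SD = 2 / 0.809 = 2.47.

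The stated 50 is consistent with an SD near 2.5. The sample size itself is not in dispute here.

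**3. The two readings of the parenthesis.**

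- Strict: all three signs are needed. A patient without shoulder pain has not reached the scoring moment. Nothing says whether the patient is then missing, scored later or scored at the call.
- Cue: the patient's perception decides, and the three signs only help recall. A patient without pain reports 0. The bias is 0.

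**4. Illustration of the strict reading with such patients unscored.** From the documents: the 2-unit shift and 25 per arm. Assumed: SD 2.47 (step 2), control means 4 to 7, underlying normal pain with the active mean 2 lower, scores rounded and limited to 0–10, and every patient scoring 0 dropped.

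Share scoring 0 = Φ((0.5 − mean)/2.47). At control mean 6 this is Φ(−2.23) = 1.3% of controls and, at active mean 4, Φ(−1.42) = 7.8% of active patients.

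Mean after dropping = recorded mean / (1 − share scoring 0). At control mean 6 the rounded and limited distributions have means 5.95 and 4.05, a difference of 1.91 before rounding the means. After dropping they are 6.03 and 4.39, a difference of 1.64.

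| Assumed control mean | Expected zeros of 25, active / control | Difference, all scored | Difference, zeros dropped | Loss | Power, all scored → zeros dropped |
|---|---|---|---|---|---|
| 4 | 6.8 / 2.0 | 1.76 | 1.25 | 0.51 | 0.78 → 0.50 |
| 5 | 3.9 / 0.9 | 1.87 | 1.47 | 0.40 | 0.79 → 0.62 |
| 6 | 2.0 / 0.3 | 1.91 | 1.64 | 0.27 | 0.79 → 0.70 |
| 7 | 0.9 / 0.1 | 1.87 | 1.72 | 0.15 | 0.79 → 0.75 |

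Power is by simulation with a pooled t-test. The recorded difference is below 2.0 even with all patients scored, because the scale stops at 0 and 10. With an assumed SD of 2.0, the losses at means 4 to 7 are 0.47, 0.30, 0.15 and 0.06, and power falls from 0.93 to 0.75, 0.86, 0.90 and 0.92. Scientific Background ranks this surgery among the most painful, which favours the higher means and the smaller losses. Scoring at a later, treatment-dependent time was not modelled, and its direction is unknown.

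**The case against.** The strongest reply is that the plan does not require the strict reading. The governing words are those about the patient's own perception. The parenthesis can be taken as help in recalling the moment, the NRS already has a 0 for no pain, and the t-test plan excludes nobody. This stands: under that reading there is no bias, and the text permits it. It does not remove the gap, because the protocol does not say that the cue reading applies and so leaves the choice to the caller.

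On the time point, one can say that 24 hours only marks when the phone call happens, and that the other two sections agree with each other. That may well be the intention. But the sentence in Study Objectives attaches 24 hours to the pain score, and a reader of that section alone would analyse a different outcome.

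The size is also open to attack, rightly. Every figure in the table needs an assumed mean and an assumed exclusion, and the largest loss comes from the least plausible mean. In this model, dropping zeros works against the drug, so it does not manufacture a positive result.

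A reader might infer the reverse, that dropping pain-free patients inflates the effect. With equal shares of 10% in both arms and whole-arm means of 6 and 4, the difference would become 2 / (1 − 0.10) = 2.22. The documents give no support for equal shares under an effective drug. Any power gain computed this way depends largely on holding the whole-arm SD at 2.47, which forces the remaining controls to an SD of √((36 + 2.47²)/0.9 − (6/0.9)²) ≈ 1.53. I place no weight on it.

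**Conclusion.** The inconsistency in the primary outcome is certain and needs no assumption: one section says 24 hours, two say block resolution, and the two moments are normally at least about 10 hours apart. It is also certain that shoulder pain is among the signs describing the scoring moment and that no rule covers a patient without it.

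The bias is only possible. A reader might infer that the plan excludes pain-free patients, or that the primary comparison is biased in a known direction. The documents support neither. No section drops such patients, and none says that they score 0. Under the cue reading the bias is nil. Under the strict reading with such patients unscored, the illustration at control means 6 to 7 gives a loss of 0.27 to 0.15 NRS units and power of about 0.70 to 0.75 instead of 0.79, with larger losses at lower means. Those figures rest on the implied SD, the assumed means and the assumed exclusion.

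This should be fixed. The defect in the text is clear; its numerical effect is not.

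**What to change.** Make Study Objectives, Study Design and Methods and Statistical Considerations name one primary outcome at one time point. Block resolution is the one that the last two already share.

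- **If block resolution is kept:** state that onset of shoulder pain is not required for the block to count as resolved, that resolution is judged by return of sensation and movement, and that every randomised and treated patient who is reached gets a score, with no pain scored 0. State also how a patient whose block has not resolved by the call is scored. An entry of score and clock time in the existing 72-hour diary would help recall but is optional.
- **If 24 hours is chosen:** state what it is counted from, since the call is counted from leaving the hospital. State that no pain scores 0, and restate the sample-size assumption for that time point.

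The cost is a few sentences. Keeping block resolution has one real downside: the shoulder sign is the only one of the three located at the operated joint, so without it a patient with residual block there might be scored slightly early. Choosing 24 hours avoids that but requires the restated assumption.

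### Does the 2-unit benchmark for clinical importance need a pre-specified confidence interval behind it?

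*Combined protocol and SAP*

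**What the plan says.** Everything on this point is in the Statistical Considerations section of the combined protocol and SAP.

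- **Design difference.** The section reports that published minimum important differences for acute, postoperative and "shoulder-related pain range between 1 and 2 (out of 10"). It takes the top of that range: "We chose a change in the score of 2 units to represent a clinically important improvement in pain control".
- **Sample size.** "To detect a decrement of 2 units or more with a two-tailed significance level of 0.05 and a power of 0.8", the section states that "a sample size of 50 is required, 25 in each group". No SD is given.
- **Analysis.** Continuous measures, pain scores among them, are summarised as mean and "standard deviation, and compared using t-tests".
- **Two criteria.** "A two-tailed p value of <0.05 is considered to reflect statistical significance". Separately, "a difference in the primary outcome of 2 or more on the NRS scale is our threshold for clinically meaningful change".

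No confidence interval, or other direct measure of precision for the difference, appears anywhere in the document. Nor does the section say how the 2-unit benchmark is to be applied. The most natural reading is that the observed difference in means is compared with 2.

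**The concern.** The p-value tests a difference of zero, not of 2. If the clinical label rests on the point estimate, the plan attaches no uncertainty to its statement about the size of benefit, and 25 per group gives an estimate that is imprecise relative to a threshold of 2. Two trials observing 1.8 and 2.2 would carry almost the same evidence, yet only the second would reach the benchmark. A treatment whose true effect is below 2 could also reach it by chance. What is at stake is how strongly the trial can speak about the size of benefit. The superiority test is not in question.

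**Working it through.** **1. Inputs.** From Statistical Considerations: difference 2, two-sided alpha 0.05, power 0.8, 25 per group. The SD is an assumption, examined from 1.5 to 3.5.

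**2. The plan's own figure.** Without an SD, 25 per group cannot be reproduced directly, so I solve for the SD.
- Normal approximation with SD 2.5: n = 2 × (1.960 + 0.842)² × 2.5² / 2² = 24.5, that is 25 per group.
- Two-sample t-test (48 df): 25 per group gives exactly 80% power at a standardised difference of 0.809, so SD = 2 / 0.809 = 2.47.

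The two agree closely. I use 2.47 as the central value, though other combinations (for example SD 2.25 with a 20% dropout allowance) would also give 25.

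**3. Precision of the difference.** Half-width = t(0.975, 48) × SD × √(2/25) = 2.011 × SD × 0.2828.

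| SD | Standard error | 95% half-width | Interval if 2.0 is observed | p if 2.0 is observed |
|---|---|---|---|---|
| 1.5 | 0.424 | 0.85 | 1.15 to 2.85 | <0.001 |
| 2.0 | 0.566 | 1.14 | 0.86 to 3.14 | <0.001 |
| 2.47 | 0.699 | 1.41 | 0.6 to 3.4 | 0.006 |
| 3.0 | 0.849 | 1.71 | 0.29 to 3.71 | 0.023 |
| 3.5 | 0.990 | 1.99 | 0.01 to 3.99 | 0.049 |

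At SD 2.47, an observed 1.8 has interval 0.39 to 3.21 (p = 0.013) and an observed 2.2 has 0.79 to 3.61 (p = 0.003). Both intervals contain 2.

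**4. Is information lost?** No. With equal groups the interval is the difference in means ± 2.011 × √((SD₁² + SD₂²)/25). Every term is a quantity the plan already reports, and the t-test is built on the same standard error.

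**5. Can the benchmark be reached without evidence of any effect?** An observed difference of 2 is significant for any SD up to 2 / (2.011 × 0.2828) = 3.52. In that range a trial that reaches the benchmark has also rejected zero. With no true difference, the chance of observing 2 or more is 1 − Φ(2/0.699) = 0.2% at SD 2.47, and 1 − Φ(2/0.990) = 2.2% at SD 3.5.

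**6. Benchmark on the estimate or on the whole interval.** The first is 1 − Φ((2 − true)/SE). The second, lower limit at or above 2, is a noncentral-t probability.

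| True difference (SD 2.47) | Estimate at or above 2 | Whole interval at or above 2 |
|---|---|---|
| 1.0 | 7.6% | 0.04% |
| 1.5 | 24% | 0.4% |
| 2.0 | 50% | 2.5% |
| 3.0 | 92% | 29% |

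Over SD 1.5 to 3.5, the 24% runs from 12% to 31%, the 7.6% from 0.9% to 16%, and the 29% from 64% down to 17%. The 50% and 2.5% at a true 2 hold for any SD.

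**7. What the interval rule would demand.** At SD 2.47 the observed difference must reach 2 + 1.41 = 3.41. A true difference of about 4 is needed for 80% success. With a true difference of 3, 80% power needs about 97 per group (64 at SD 2.0, 143 at SD 3.0), against 25 planned.

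**The case for a change.** The strongest argument for acting is that the benchmark is the trial's own second criterion, so how it is read should be fixed before the data are seen. A reader can rebuild the interval, but that does not tell them which rule the investigators meant. At a true difference of 1.5, about 24% of trials would reach the benchmark, and nearly all of their intervals would extend below 2. Adding an interval costs a sentence.

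Part of this stands. The plan is silent on the interval, and an estimate near 2 should not be presented as proof of a 2-unit effect. A report that shows the interval will be more informative than one that does not.

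The rest carries less weight. The comparison of 24% with 0.4% sets two different claims side by side. The plan calls 2 units a threshold for meaningful change; it does not say that an estimate of 2 proves the true effect is at least 2. A true effect of 1.5 also lies inside the 1-to-2 range that the section itself cites for minimum importance, so calling such a result meaningful is not clearly wrong. The contrast between 1.8 and 2.2 shows only that any cut-off separates neighbouring values. An interval rule has a cut-off too, at about 3.4 when the SD is 2.47.

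**Conclusion.** The concern is accurate about what is missing, but it does not call for a change. It has two parts.

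**Reporting an interval.** This is a gap that an analyst fills as a matter of course. The interval is standard output of the planned t-test and follows from the planned summaries. Its presence or absence changes no estimate, p-value, sample size or superiority conclusion.

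**Basing the clinical label on the interval.** This would change a conclusion, and it is a trade-off on which reasonable statisticians differ. It turns a benchmark read beside p < 0.05 into superiority by a margin equal to the design difference. That requirement is met 2.5% of the time when the design assumption is exactly true, and about 95% of results would then be inconclusive. Keeping the benchmark on the estimate is defensible for a trial of 50.

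The 2.5% and 95% do not depend on the SD. The other figures rest on two equal groups of 25, roughly normal mean differences, and an SD back-solved as 2.47. Half-widths run from 0.85 to 1.99 over SD 1.5 to 3.5, and the conclusion holds throughout. The unstated SD is a separate matter and serves here only as a labelled assumption.
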